7.2 Treatment (2/2/16)

7.2.1 Cisplatin:

Weeks 2-7 with concurrent radiation therapy and lapatinib/placebo: Patients will receive cisplatin, 100 mg/m², administered intravenously on days 8 and 29 of the treatment course (Note: cisplatin given within 24 hours of days 8 and 29, e.g. due to holidays, is acceptable). Weekends count as days. Cisplatin can be given before or after the fraction of radiation that is given on the same day. If radiation is held for more than 2 days (for any reason), cisplatin may be held as well until radiation therapy resumes.

See Section 7.6.1 for dose modification for weight loss. Use the actual body weight for all patients. Dose modification for obesity is not recommended.

7.2.1.1 High dose cisplatin is a highly emetogenic regimen with significant incidence of delayed nausea and vomiting. Institutional guidelines for highly emetogenic regimens should be followed. In the absence of such guidelines:

- For acute nausea and vomiting, premedication should include a 5-HT₃ antagonist, such as granisetron 1 mg iv.; ondansetron, up to 16 mg iv; or palonosetron, 0.25 mg

iv.; plus a corticosteroid, such as dexamethasone, up to 20 mg iv.. Palonosetron has a longer half life (40h) than the first generation 5HT3 antagonists.

- Breakthrough nausea and vomiting should be managed at the discretion of the medical or radiation oncologist. Delayed nausea and vomiting (greater than 24 hours after chemotherapy administration) may be managed by the addition of aprepitant concurrently or with metoclopramide and dexamethasone. Potential delayed nausea regimens include:
 1. The NK-1 antagonist, aprepitant (125 mg p.o.), may be added for prevention of delayed emesis on the day of cisplatin administration and for 2 consecutive days thereafter (80 mg, 80 mg p.o.), with a corticosteroid, such as dexamethasone on days 1, 2, and 3 after cisplatin. Dexamethasone should be reduced on day 1 to 12 mg and delivered at up to 8 mg total daily for up to 4 days total. 5HT3 antagonist (e.g. granisetron, ondansetron) may be given for 3 days, only if palonosetron was not given prior to chemotherapy. Fosaprepitant (115 mg iv. x 1) may be used instead of aprepitant on day 1, 30 minutes before cisplatin; if used, fosaprepitant may be used with or without aprepitant day 2 and 3, and dexamethasone will be given as described above.

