7.6 Dose Modifications (3/22/16)

7.6.1 Cisplatin Modifications, Day 29

7.6.1.1 Neutropenia: If on the day of scheduled treatment with cisplatin the absolute neutrophil count (ANC) is < 1200, hold treatment until ANC ≥ 1200, then treat at 100% dose. Neutropenic fever will require permanent 25% dose reduction. Per CTCAE, v. 4, febrile neutropenia is described as ANC < 1000/mm³ with a single temperature of >38.3 degrees C (101 degrees F) or a sustained temperature of ≥ 38 degrees C (100.4 degrees F) for more than 1 hour.

7.6.1.2 Thrombocytopenia: If on the day of scheduled treatment with cisplatin the platelet count is < 75,000, hold treatment until platelets are > 75,000, then treat at 100% dose. Thrombocytopenia that results in bleeding will require a 25% dose reduction.

7.6.1.3 Neurotoxicity: If any signs of grade 3 or greater neurotoxicity occur, discontinue cisplatin. Continue radiation therapy (RT) and lapatinib/placebo.

7.6.1.4 Renal Adverse Events: Cisplatin should be administered on the scheduled day of treatment using the following guidelines. **Note:** If creatinine is > 1.3 mg/dl, clearance must be calculated (Cockcroft-Gault) in order to make dose adjustment. If the calculated nomogram is 50 mL/min or above, a 24-hour urine collection is not needed, but if the calculation is less than 50 mL/min, a 24-hour urine collection is mandated and the cisplatin will be determined as follows:

Serum Creatinine	Creatinine Clearance	Cisplatin Dose
≤ 1.5 mg/dl OR	> 50 ml/min.	100 mg/m ²
> 1.5 mg/dl AND	40-50 ml/min.	50 mg/m ²
> 1.5 mg/dl OR	< 40 ml/min.	Hold drug*

*Cisplatin should be held (but RT continued), and the creatinine measured weekly. If the serum creatinine is < 1.5 mg/dl or creatinine clearance is > 50 ml/min, then the second dose of cisplatin can be given at the reduced dose of 50 mg/m². Also see Section 7.6.1.6 below.

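### The day-29 cisplatin renal dose table (7.6.1.4) has overlapping rows, so some creatinine and clearance values direct both a dose and a hold

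*Combined protocol and SAP*

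**What the plan says.** Section 7.2.1 plans cisplatin 100 mg/m², "administered intravenously on days 8 and 29 of the treatment course". Section 7.6.1 governs modification of the day-29 dose, and 7.6.1.4 deals with renal function.

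The note in 7.6.1.4 applies when creatinine exceeds 1.3 mg/dl. In that case "clearance must be calculated (Cockcroft-Gault) in order to make dose adjustment". If the calculated value is 50 ml/min or above, no 24-hour urine collection is needed. If it is lower, "if the calculation is less than 50 mL/min, a 24-hour urine collection is mandated and the cisplatin will be determined as follows".

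The table has three rows:
- Row 1: creatinine ≤1.5 OR clearance >50 gives 100 mg/m².
- Row 2: creatinine >1.5 AND clearance 40-50 gives 50 mg/m².
- Row 3: creatinine >1.5 OR clearance <40 means hold.

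The footnote covers a held dose. Creatinine is measured weekly, and if it is <1.5 or clearance is >50, "then the second dose of cisplatin can be given at the reduced dose of 50 mg/m²". Section 7.6.1.6 omits the second dose after a hematologic or renal delay of more than 21 days. Neither section says which row prevails when two apply.

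**The concern.** A dose table should send each set of laboratory values to one action. Here rows 1 and 3 are each joined by OR, and row 2 sits between them joined by AND, so the rows overlap. Two sites with identical patients could give a full dose and a hold, or a half dose and a hold, and each could cite a row.

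The drug is nephrotoxic: section 7.3.5 lists raised creatinine, impaired clearance and renal tubular damage among its expected adverse events. Day 29 is one of only two planned doses. After a full day-8 dose, the planned total is 100 + 100 = 200 mg/m². With a restart at half dose it is 100 + 50 = 150, and with the second dose omitted it is 100. Which total a patient receives could depend on the row the site reads.

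**Working it through.** **Inputs.** The three rows, note and footnote come from 7.6.1.4. The Cockcroft-Gault formula comes from 3.1.7.1: for a man, (140 − age) × weight / (72 × creatinine). There is no figure in the plan to reproduce; this is a check of logic.

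**Step 1: apply the rows as written to every region.**

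| Creatinine (mg/dl) | Clearance (ml/min) | Rows met | Instruction |
|---|---|---|---|
| ≤1.5 | <40 | 1 and 3 | 100 mg/m² and hold |
| ≤1.5 | 40-50 | 1 | 100 mg/m² |
| ≤1.5 | >50 | 1 | 100 mg/m² |
| >1.5 | <40 | 3 | hold |
| >1.5 | 40-50 | 2 and 3 | 50 mg/m² and hold |
| >1.5 | >50 | 1 and 3 | 100 mg/m² and hold |

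Every patient who meets row 2 has creatinine >1.5 and so meets row 3. Row 2 never acts alone.

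**Step 2: narrow to what the note requires.**
- Clearance is required only when creatinine exceeds 1.3. The conflict in the first line therefore arises in required practice for creatinine above 1.3 and up to 1.5.
- If Cockcroft-Gault is below 50, the value to read against the table is the 24-hour measurement.
- The wording that leads into the table is attached to the below-50 branch. If the table serves only that branch, the last line could arise only from a 24-hour result above 50. If it serves all patients, the last line conflicts directly.

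**Step 3: can such values occur?** For assumed men:
- Age 70, 50 kg, creatinine 1.4: 70 × 50 / (72 × 1.4) = 34.7. Rows 1 and 3, if the 24-hour value is also below 40.
- Age 50, 60 kg, creatinine 1.6: 90 × 60 / (72 × 1.6) = 46.9. Rows 2 and 3, if the 24-hour value is also 40-50.
- Age 50, 85 kg, creatinine 1.6: 90 × 85 / (72 × 1.6) = 66.4. Rows 1 and 3, if the table applies above 50. No collection is needed.

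Renal eligibility in 3.1.7.1 is creatinine <1.5 or clearance ≥50, so the first and third men could enter the trial with these values.

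**Step 4: footnote.** A patient held for clearance <40 with creatinine <1.5 already satisfies the restart condition through creatinine. With creatinine 1.4 and measured clearance 35, row 1 says 100 mg/m², row 3 says hold, and the footnote allows 50 mg/m².

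**Step 5: try the obvious tie-breakers on the three conflicting regions.**

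| Region | First matching row | Most cautious row | Clearance column alone |
|---|---|---|---|
| ≤1.5, <40 | 100 | hold | hold |
| >1.5, 40-50 | 50 | hold | 50 |
| >1.5, >50 | 100 | hold | 100 |

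The tie-breakers disagree in every region. Dosing on clearance alone would also change a region that is now unambiguous: creatinine ≤1.5 with clearance 40-50 would go from 100 to 50 mg/m².

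**The case against.** The best defence is that a sensible clinician can make the table work. Read from the top with the first match winning, it gives one dose everywhere. The clearance column alone is also exclusive, and the note ties dose adjustment to clearance. The either/or form of row 1 resembles the eligibility rule and the footnote, so the OR there may be deliberate. The table is introduced as guidelines and touches one dose of two.

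These points show that a rule was intended, but not which one. For creatinine 1.4 and clearance 35, first match gives 100 mg/m² and the clearance column gives hold, and the protocol adopts neither reading.

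The limits on scope do stand: the 24-hour measurement takes over below 50, clearance is required only above creatinine 1.3, and the conflict above 50 depends on how the lead-in is read.

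A reader might also infer that treatment compliance (13.2.4) could not be scored consistently. The documents do not support this. Section 7.8 gives the chemotherapy review of all patients to the Principal Investigator, and one reviewer can apply one reading throughout.

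**Conclusion.** The table contradicts itself as written. Two of six regions conflict on any reading of its scope: creatinine ≤1.5 with clearance <40 (full dose and hold), and creatinine >1.5 with clearance 40-50 (half dose and hold). A third, creatinine >1.5 with clearance >50 (full dose and hold), conflicts if the table applies at all clearance values. The worked patients are assumed, and the two with calculated clearance below 50 count only if the 24-hour value falls in the same band.

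The documents do not show how many patients would fall in these regions, so no frequency is claimed. It would be tempting to carry the point through to the trial's main result. The documents give no basis for that: both arms use the same table under a double blind, and the sample size, the significance levels and the PFS log-rank test do not depend on it. What is affected is the safety of the day-29 dose and the consistency of dosing across sites.

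**What to change.** Make the rows mutually exclusive at the existing thresholds, and have the study chair confirm the intended rule. For example:
- Clearance <40, whatever the creatinine: hold.
- Creatinine >1.5 and clearance 40-50: 50 mg/m².
- Clearance >50, or creatinine ≤1.5 with clearance ≥40: 100 mg/m².

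In the order of the six-region table, this gives hold, 100, 100, hold, 50, 100: one action each. It keeps the three regions that are already unambiguous.

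State that the table applies at all clearance values and that the 24-hour result is used when Cockcroft-Gault is below 50. Say also that creatinine of 1.3 or less, where no clearance is required, keeps the row 1 dose.

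Reword the footnote so that values that trigger a hold cannot also satisfy restart. One way is to require clearance of at least 40 in addition to the present restart condition.

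The cost is one amendment or site memo. A held patient would need a current clearance before restart. Sample size and planned analyses do not change.

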3.1 Conditions for Patient Eligibility (9/27/16)

3.1.1 Pathologically (histologically or cytologically) proven diagnosis (from primary lesion and/or lymph nodes) diagnosis of squamous cell carcinoma of the oropharynx, hypopharynx, or larynx;

3.1.2 For patients with an oropharynx primary, the tumor must be negative for p16 by immunohistochemistry;

3.1.3 Selected stage III or IV disease: patients with T2 N2-3 M0, T3-4 any N M0 are eligible; in addition, p16 negative oropharynx cancer T1 N2b, N2c, or N3; and hypopharynx cancer patients with T1-2 any N+ are eligible, including no distant metastases, based upon the following minimum diagnostic workup:

3.1.3.1 History/physical examination within 28 calendar days prior to registration, including an examination by a Medical Oncologist and Radiation Oncologist and documentation of the patient's weight;

3.1.3.2 Examination by an ENT or Head & Neck Surgeon, including laryngopharyngoscopy (mirror and/or fiberoptic and/or direct procedure) within 42 days prior to registration;

3.1.3.3 Chest CT scan, or PET/CT scan within 42 calendar days prior to registration to rule out metastatic disease;

3.1.3.4 Contrast enhanced CT scan or MRI or PET/CT scan of the tumor site and neck nodes within 42 calendar days prior to registration;

3.1.3.5 EKG and ECHO or MUGA scan within 84 calendar days prior to registration;

- 3.1.4 Zubrod Performance Status 0-1 within 14 calendar days prior to registration;
- 3.1.5 Age \geq 18;
- 3.1.6 CBC/differential obtained within 14 calendar days prior to registration, with adequate bone marrow function defined as follows:
 - 3.1.6.1 Absolute neutrophil count (ANC) \geq 1,500 cells/mm³;
 - 3.1.6.2 Platelets \geq 100,000 cells/mm³;
 - 3.1.6.3 Hemoglobin \geq 8.0 g/dl (Note: The use of transfusion or other intervention to achieve Hgb \geq 8.0 g/dl is acceptable.);
- 3.1.7 Adequate renal and hepatic function within 14 calendar days prior to registration, defined as follows:
 - 3.1.7.1 Serum creatinine < 1.5 mg/dl or creatinine clearance (CC) \geq 50 ml/min within 14 calendar days prior to registration, determined by 24-hour collection or estimated by Cockcroft-Gault formula:
 - CCr male = [(140 – age) x (wt in kg)]
[(Serum Cr mg/dl) x (72)]
 - CCr female = 0.85 x (CrCl male)
 - 3.1.7.2 Total bilirubin < 2 x the institutional ULN;
 - 3.1.7.3 AST or ALT \leq 3 x the institutional ULN;

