7.6.1.5 Other Adverse Events

- Mucositis: Significant mucositis from radiation and cisplatin is expected and will not be an indication for cisplatin dose modification. No cisplatin dose reductions will be made.

- Ototoxicity: For new clinical hearing loss not requiring a hearing aid or for tinnitus that interferes with activities of daily living, treat at 50% dose reduction. For hearing loss requiring a hearing aid, discontinue cisplatin. Continue RT and lapatinib/placebo.
- If the physician is unsure about the severity of the hearing loss, an audiogram is encouraged.

7.6.1.6 If the second dose of cisplatin is delayed more than 21 days because of hematologic or renal adverse events, that dose will be omitted.

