7.8 Modality Review

The Principal Investigator, [name], will perform a Chemotherapy Assurance Review of all patients who receive or are to receive chemotherapy in this trial. The goal of the review is to evaluate protocol compliance. The review process is contingent on timely submission of chemotherapy treatment data as specified in Section 12.1. The scoring mechanism is: **Per Protocol, Acceptable Variation, Unacceptable Deviation, and Not Evaluable**. A report is sent to each institution once per year to notify the institution about compliance for each case reviewed in that year.

The Principal Investigator, [name], will perform a Quality Assurance Review after complete data for the first 20 cases enrolled has been received at RTOG Headquarters. [name] will perform the next review after complete data for the next 20 cases enrolled has been received at RTOG Headquarters. The final cases will be reviewed within 3 months after this study has reached the target accrual or as soon as complete data for all cases enrolled has been received at RTOG Headquarters, whichever occurs first.

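### The day 29 cisplatin renal table (7.6.1.4) gives two different actions in three of its six creatinine/clearance combinations, and its footnote lets creatinine alone release a hold made for low clearance.

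*Combined protocol and SAP*

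**What the plan says.** Section 7.2.1 plans two cisplatin doses of 100 mg/m², "administered intravenously on days 8 and 29 of the treatment course". Section 7.6.1 covers modification of the day 29 dose, and 7.6.1.4 is its renal rule.

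- **Note.** "If creatinine is > 1.3 mg/dl, clearance must be calculated (Cockcroft-Gault) in order to make dose adjustment". If the calculated value is 50 ml/min or above, no urine collection is needed. If it is below 50, "a 24-hour urine collection is mandated and the cisplatin will be determined as follows", and the table follows.
- **Table.** Full dose (100 mg/m²) if creatinine is 1.5 mg/dl or less OR clearance is above 50. Half dose (50 mg/m²) if creatinine is above 1.5 AND clearance is 40-50. Hold if creatinine is above 1.5 OR clearance is below 40.
- **Footnote to hold, monitoring.** "Cisplatin should be held (but RT continued), and the creatinine measured weekly".
- **Footnote to hold, release.** The condition for ending the hold reads: "If the serum creatinine is < 1.5 mg/dl or creatinine clearance is > 50 ml/min, then the second dose of cisplatin can be given". The dose released in this way is halved, to 50 mg/m².
- **Limit on delay (7.6.1.6).** "If the second dose of cisplatin is delayed more than 21 days because of hematologic or renal adverse events, that dose will be omitted".

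No order of precedence between the rows is stated.

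**The concern.** The full-dose and hold rows each join their two criteria with OR, so they can both be true for one patient. The half-dose row requires creatinine above 1.5, which alone is enough for a hold. Two sites can therefore both follow the text and act differently on the same patient.

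Cisplatin is nephrotoxic: section 7.3.5 lists raised creatinine, impaired clearance and renal tubular damage as anticipated events. This is the rule for a foreseeable toxicity. The day 29 dose is half of the planned cisplatin, and a delay of more than 21 days loses it. The chemotherapy review in 7.8 ("The goal of the review is to evaluate protocol compliance") and the secondary endpoint on compliance (13.2.4) also need one correct dose to score against.

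**Working it through.** **Inputs.** Table, Note and footnote from 7.6.1.4; Cockcroft-Gault formula from 3.1.7.1. The plan states no figure to reproduce; the check is to apply the three rows to every combination of two creatinine bands and three clearance bands.

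**Step 1: the rows and the possible readings** (Cr in mg/dl, CCr in ml/min, dose in mg/m²).

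| Cr | CCr | Rows met as written | First matching row | Most restrictive row | Clearance only |
|---|---|---|---|---|---|
| ≤ 1.5 | > 50 | 100 | 100 | 100 | 100 |
| ≤ 1.5 | 40-50 | 100 | 100 | 100 | 50 |
| ≤ 1.5 | < 40 | **100 and hold** | 100 | hold | hold |
| > 1.5 | > 50 | **100 and hold** | 100 | hold | 100 |
| > 1.5 | 40-50 | **50 and hold** | 50 | hold | 50 |
| > 1.5 | < 40 | hold | hold | hold | hold |

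Three of six combinations carry two actions. No reading leaves the whole section working:

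- *Most restrictive row:* the 50 mg/m² row is never used.
- *First matching row* (the same doses as replacing OR with AND in the hold row): creatinine of 1.5 or less gives full dose at any clearance, even below 40. The clearance and urine collection required at creatinine above 1.3 and up to 1.5 then change nothing.
- *Clearance only:* no conflicts and no gaps, but it gives 50 where the table gives only 100 (creatinine ≤ 1.5, clearance 40-50).

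**Step 2: can the conflicting combinations occur?** CCr = (140 − age) × weight / (72 × Cr) for men. Ages, weights and creatinine values are assumptions for illustration.

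- Man, 70 years, 50 kg, Cr 1.4: 70 × 50 / (72 × 1.4) = 3500 / 100.8 = 34.7. A collection is mandated; a collected value below 40 meets both 100 and hold.
- Man, 60 years, 70 kg, Cr 1.7: 80 × 70 / (72 × 1.7) = 5600 / 122.4 = 45.8. A collection is mandated; a collected value of 40-50 meets both 50 and hold.
- Cr > 1.5 with CCr > 50: if the table applies only after a calculated value below 50, this needs a collected value above 50 that disagrees with the estimate. That is possible but narrower.

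**Step 3: the footnote.** Release = Cr < 1.5 OR CCr > 50. The first man above, if held because his collected clearance is below 40, has Cr 1.4 < 1.5. The release condition is already true with clearance unchanged, and only creatinine has to be measured during the hold.

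**Step 4: dose at stake**, assuming full dose on day 8. Planned total: 2 × 100 = 200 mg/m². In the two full-dose-versus-hold combinations the total can be 200 (full), 100 + 50 = 150 (held, then released) or 100 (second dose omitted). In the half-dose combination it is 150 or 100.

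**The case against.** The best reply is that the Note puts clearance first. It requires clearance for the dose adjustment and mandates a collection when the estimate is below 50, so a clinician would dose on the measured value: above 50 full, 40-50 half, below 40 hold. This may well be the intent. But the text does not say it, every row also carries a creatinine criterion, and this reading contradicts the full-dose row at creatinine ≤ 1.5 with clearance 40-50. A site cannot derive it from the table.

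Second, the table grammatically follows the branch for a calculated value below 50. This stands, and it limits the third conflict. A reader might infer that any patient with creatinine above 1.5 and an estimate above 50 gets contradictory orders. The documents do not support that, because on this reading such a patient never reaches the table. The other two conflicts are untouched.

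Third, the footnote is permissive, the released dose is halved, and weekly weight and creatinine (Appendix I) would let a site update the estimate. That lowers the risk, but nothing requires the update, and creatinine alone remains sufficient for release.

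A reader might also infer that not requiring a clearance at creatinine of 1.3 or less is a further error. It contradicts nothing: eligibility (3.1.7.1) likewise accepts creatinine below 1.5 alone. Requiring it would be a preference that adds 24-hour collections.

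Finally, compliance is scored by one reviewer with an acceptable-variation category (7.8), which softens the scoring consequence.

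**Conclusion.** The point holds. As written, 3 of 6 combinations carry two actions, one of them only on a discordant collected value if the table is confined to estimates below 50. The half-dose row lies wholly inside the hold row, and a hold for clearance below 40 can be released on creatinine alone. This rests on a literal reading of AND and OR; these words are intact in the table.

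This is a matter of patient safety and consistent dosing. A reader might infer a biased treatment comparison; the documents do not support that, since the same rule applies in both blinded arms and neither the PFS definition nor its test uses this table. How many patients would fall in the conflicting combinations cannot be computed from the documents.

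**What to change.** 1. **Table.** Delete the creatinine criterion from the hold row, so that hold means clearance below 40 at any creatinine. Add to the 100 mg/m² row an exception for clearance below 40. Each combination then has one action:

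| | CCr > 50 | CCr 40-50 | CCr < 40 |
|---|---|---|---|
| Cr ≤ 1.5 | 100 | 100 (as now) | hold |
| Cr > 1.5 | 100 | 50 | hold |

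A patient with creatinine of 1.3 or less and no clearance value still gets 100 mg/m², so no gap opens.

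2. **Footnote.** Remove release on creatinine alone. Require a repeat clearance (Cockcroft-Gault or 24-hour) above a stated value before the held dose is given at 50 mg/m².

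**Cost.** Edits to two table rows and one footnote, plus a repeat clearance in held patients only. A few second doses will be held or delayed, and some may pass the 21-day limit and be omitted. These can include patients admitted on creatinine alone whose clearance was already below 40 when they had full dose on day 8; the present hold row already covers them, but so does the full-dose row.
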